5.4.2 Pharmacokinetic Parameters Calculation and Summary

The pharmacokinetic (PK) parameters of the concentration data for AZD4320 and its metabolites (if applicable) will be derived using non-compartmental methods in Phoenix® WinNonlin® Version 8.1 or higher as data applicable. The PK parameters are calculated / estimated according to AstraZeneca standards

Derived PK parameters will be summarized by cycle, separately per dose level/cohort. The following summary statistics will be presented for the estimated PK parameters, as appropriate:

- Gmean (calculated as $\exp[\mu]$, where μ is the mean of the data on a logarithmic scale)
- gCV (calculated as $100 \sqrt{[\exp(s^2)-1]}$, where s is the standard deviation of the data on a log scale)
- Gmean + gSD (gSD calculated as $\exp[\mu \pm s]$)
- Gmean - gSD
- Arithmetic mean calculated using untransformed data
- Standard deviation calculated using untransformed data
- Minimum
- Median
- Maximum
- Number of observations

The following rules will be followed with regards to the number of decimal places and presentation of data in the tables and listings for PK parameters:

- Individual PK parameters will be presented to four significant digits, with the exception of t_{max} , which will be presented to two decimal places.
- Parameters derived directly from source data (e.g. C_{max}) shall be reported with the same precision as the source data (if this is not four significant digits).
- The mean, geometric mean, median and SD values will be reported to four significant digits, all other descriptive statistics will be reported to three significant digits except for CV% which will be presented to one decimal place.

- For t_{max} the minimum and maximum will be presented to two decimal places and all other descriptive statistics will be presented to three decimal places.
- Estimates and confidence intervals in the form of percentages will be presented to two decimal places.

5.4.3 Criteria for Handling Concentrations Below the Limit of Quantification or Missing Concentrations in Pharmacokinetic Analysis

For the non-compartmental analysis (NCA) and individual plot, if a BLQ value occurs before the first measurable concentration, it will be treated as zero. Thereafter, BLQ values will be treated as missing for PK analysis, with special situations described below. The following rules apply with special situations defined below:

- Where 2 or more consecutive concentrations are BLQ at the end of a profile, the profile will be deemed to have terminated and any further quantifiable concentrations will be set to missing for the calculation of the PK parameters unless they are considered to be a true characteristic of the profile of the drug.
- If an entire concentration-time profile is BLQ, the profile will be excluded from the PK analysis.
- If a pre-dose measurement for the first dose of cycle 1 is missing it will be set to zero for a single dose, or to the minimum observed concentration for a repeat dose.

5.4.4 Treatment of Outliers in Pharmacokinetic Analysis

If a value is considered to be anomalous due to being inconsistent with the expected PK profile, it may be appropriate to exclude this point from the PK analysis. However, the exclusion of data must have strong justification and will be documented in CSR.

Quantifiable pre-dose concentration values in the first dosing of cycle 1 (i.e., the first ramp-up dose) will be considered anomalous and set to missing for the PK analysis.

5.5 Immunogenicity

Refer to the individual modules.

5.6 Safety Analyses

The domain safety covers exposure, adverse events, clinical laboratory, vital signs, ECG, B-symptoms, and tumour lysis syndrome (TLS).

Tables will be provided for the SAF, listings are provided for all patients or the SAF depending on the availability of data.

All safety analysis will be presented by dose level/cohort. The results from the ramp-up period will be presented separately.

5.6.1 Exposure

5.6.1.1 Definitions and Derivations

- Total duration of exposure is defined by the last date of actual dosing (i.e., a dose > 0 mg/L was given) in the last cycle plus 28 days (28 is by default, the number of days in a cycle or until the next scheduled dose, there 7 days during the intrapatient ramp-up and 21 days thereafter) minus the date of first treatment study treatment.
 - For patients who die whilst on study treatment or if a DCO occurs, duration of exposure (months/weeks) is defined as date of death/DCO (whichever occurs first) minus the date of first treatment plus 1 day.
- Actual treatment duration = total treatment duration, excluding dose interruptions not in accordance with the protocol, and any planned no dose periods.
- Dose intensity of study treatment is addressed by considering relative dose intensity (RDI), where RDI is the percentage of the actual dose delivered relative to the intended dose through to treatment discontinuation. More specifically, RDI is defined as follows:
 - $RDI = 100\% \times d/D$, where d is the actual cumulative dose delivered up to the actual last day of dosing and D is the intended cumulative dose up to the actual last day of dosing. D is the total dose that would be delivered, if there were no modification to dose or schedule.
- The duration of an interruption will be calculated as [date/time treatment resumed – date/time treatment stopped]. Overall duration of interruption will be calculated as the sum of all individual interruptions during the study.

Duration of dose delays will be derived for doses indicated as being delayed on the eCRF. For each individual dose, the duration for dose delay is the number of days the dose was received outside of the original planned dosing schedule. Overall duration of dose delays will be calculated as the sum of all individual dose delays during the study.

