10.6.6.2 Dose Expansion

Cohorts may open either in parallel or sequentially at the Sponsor's discretion. The dose expansion part of the study (Part B) will enrol up to approximately [redacted] patients. After determining the RP2D in Module 1 Part A (dose escalation), the following separate cohorts may be opened at the RP2D in Module 1 Part B.

- **Cohort B1:** Approximately [redacted] response-evaluable patients with R/R MCL
- **Cohort B2:** Approximately [redacted] response-evaluable patients with R/R FL or MZL
- **Cohort B3:** Approximately [redacted] response-evaluable patients with R/R DLBCL

Following an initial ramp-up during Week 1, AZD0466 will be administered based on a weekly dosing schedule for 2 years or until disease progression, initiation of alternative anticancer therapy, unacceptable toxicity, withdrawal of consent, or other reasons to discontinue study intervention, whichever occurs first. In the event of liver or haematologic toxicities, a 2-weekly dosing schedule may be considered. In the absence of toxicities, a 2-weekly dosing schedule may also be considered after discussion with the Sponsor. For patients who are responding and do not experience unacceptable toxicities, continuation of treatment may be considered by the Investigator and Sponsor.

All patients should be followed for survival every 3 months until death. Patients who discontinue treatment due to unacceptable AEs should be followed until resolution or stabilisation of the AE, then for response and survival. Patients who achieve a CR will be followed for relapse of disease until death.

If the interim analysis of Part B meets the pre-set target value for monotherapy expansion in Cohorts B1 and B2, additional patients will be enrolled in these cohorts.

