8.1 Schema

The schema for Module 1 Part A and Part B is illustrated in [Figure 1](#).

Figure 1 Module 1 Schema

^a Alternative dosing schedule: option of dose reduce and/or change in dosing schedule from weekly to every 2 weeks based on emerging safety data.

B-NHL = B-cell non-Hodgkin lymphoma; DL = dose level; DLBCL = diffuse large B-cell lymphoma; FL = follicular lymphoma; MCL = mantle cell lymphoma; MTD = maximum tolerated dose; MZL = marginal zone lymphoma; RP2D = recommended Phase II dose; R/R = relapsed/refractory.

In part A, the initial dose levels will be set according to nonclinical modelling and data from previous studies with an intra-patient dose ramp-up to mitigate the risk of TLS. The intra-patient ramp-ups will involve beginning at a specified lower dose and rapidly increase the dose to reach target value by Day 8. For example, in dose level 1, at Cycle 1 Day 1 AZD0466 will be administered at 150 mg followed by 300 mg at Cycle 1 Day 4 and reaching target dose of 600 mg at Cycle 1 Day 8. Thereafter, weekly dosing would continue at 600 mg. Each cycle is 28 days with Cycle 1 consisting of ramp-up to achieve the target dose level and then 3 doses at target level on Days 8, 15, and 22 with a 28-day DLT period (refer to Section 10.6.6.2 of the CSP for details).

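### The total exposure rule in SAP 5.6.1.1 contradicts itself: its default 28-day add-on overstates duration by up to 21 days on weekly dosing, while its own next-dose wording does not

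*SAP*

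**What the plan says.** The general rule is in SAP 5.6.1.1. It takes the last date on which a non-zero dose was given "in the last cycle plus 28 days" and subtracts the date of first treatment. A parenthesis explains the 28 as "the number of days in a cycle or until the next scheduled dose, there 7 days during the intrapatient ramp-up and 21 days thereafter".

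A sub-rule follows: "For patients who die whilst on study treatment or if a DCO occurs, duration of exposure (months/weeks) is defined as date of death/DCO", whichever is earlier, minus the first treatment date plus 1 day. It has no add-on.

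SAP 11.7.1, the Module 1 exposure section, only points back to the core text. SAP 5.6.1.2 tabulates total and actual duration in months and, separately, the number of cycles received. SAP 5.6 adds: "The results from the ramp-up period will be presented separately".

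The schedule is in SAP 8.1 and, in the same terms, in Protocol 10.6.6.1. In the dose level 1 example the first dose is on Cycle 1 Day 1, "followed by 300 mg at Cycle 1 Day 4 and reaching target dose of 600 mg at Cycle 1 Day 8", "then 3 doses at target level on Days 8, 15, and 22". After that: "Thereafter, weekly dosing would continue at 600 mg". Protocol 10.6.6.2 allows an exception: "In the event of liver or haematologic toxicities, a 2-weekly dosing schedule may be considered".

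Protocol 9.4.1 gives a different formula, last dose date minus first dose date, in a parenthesis after total exposure and total time on study. SAP Sections 3 and 9 declare no change from the protocol's planned analyses.

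**The concern.** The parenthesis gives the add-on two meanings, a cycle length and the time to the next dose, as if they were the same number. They would be if the drug were given once per 28-day cycle. Here it is given weekly, so a cycle length counted from the last dose normally runs past the end of the cycle. The 7 and 21 do not repair this. Seven days is the weekly gap but is attached to ramp-up, and 21 days matches no gap in the schedule.

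Total duration is summarised by dose level and cohort. A fixed excess weighs most on patients who stop early. It applies to patients who stop for toxicity or progression but not to those who die on treatment or are still on treatment at the data cut-off. The duration table would also disagree with the cycle count beside it: one completed cycle would sit next to 49 / 28 = 1.75 cycles of duration.

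**Working it through.** **Inputs.** Cycle length 28 days; dose days 1, 4, 8, 15 and 22 in Cycle 1 (SAP 8.1, Protocol 10.6.6.1); Days 1, 8, 15 and 22 of later cycles (Protocol Table 14); add-on of 28 days (SAP 5.6.1.1).

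**The plan's own figure.** 28 reproduces as the days in a cycle. It does not reproduce as the days to the next scheduled dose: successive gaps are 3, 4, 7, 7, 7 and so on, and the 2-weekly option gives 14.

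**Formulas.** Let the first dose be study day 1 and the last dose study day L.
- Printed default: L + 28 − 1 = L + 27.
- Next scheduled dose, weekly: L + 7 − 1 = L + 6.
- Cycle length counted from Day 1 of the last cycle n: 28n. The SAP does not write this formula. It is the comparator if 28 is meant as the length of the last cycle.

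| Last dose | L | Default | Next dose | Cycle basis |
|---|---|---|---|---|
| Cycle 1 Day 22 | 22 | 49 | 28 | 28 |
| Cycle 2 Day 1 | 29 | 56 | 35 | 56 |
| Cycle 2 Day 8 | 36 | 63 | 42 | 56 |
| Cycle 2 Day 15 | 43 | 70 | 49 | 56 |
| Cycle 2 Day 22 | 50 | 77 | 56 | 56 |
| Cycle 6 Day 22 | 162 | 189 | 168 | 168 |

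**Completed cycles.** The last dose is on Day 22 of cycle n, so L = 28(n − 1) + 22 = 28n − 6. The default gives 28n + 21. Both other bases give 28n, so the excess of 21 days does not depend on the comparator. It is 21/28 = 75% at one cycle, 21/56 = 37.5% at two and 21/168 = 12.5% at six. In months, 21 / (365.25/12) = 0.69.

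**Incomplete last cycle, weekly.** Against the next-dose basis the excess is still 28 − 7 = 21 days. Against the cycle basis it is 0, 7, 14 or 21 days for a last dose on Day 1, 8, 15 or 22, so the default agrees with the cycle length only when the last dose is Day 1 of a cycle.

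**Other cases.**
- 2-weekly dosing: excess over the next-dose basis 28 − 14 = 14 days.
- Stopping in ramp-up: the default gives 28 days after the Day 1 dose and 31 after the Day 4 dose, against 3 and 7 days to the next scheduled dose.
- Death on treatment on Day 28, last dose Day 22: the sub-rule gives 28 − 1 + 1 = 28 days.
- Protocol 9.4.1 formula, last dose Day 22: 22 − 1 = 21 days.

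**The case against.** The strongest reply is that the sentence already contains the right rule. A programmer who follows its next-dose wording adds 7 on weekly dosing and gets 28 days for one cycle. That stands. A reader might infer that such a patient will certainly be reported at 49 days; the text does not support that certainty. It does print 28 as the default, so 49 is what the literal formula yields.

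A reader might also take 21 as the add-on after ramp-up, giving 22 + 21 − 1 = 42 days, an excess of 14. This is a weak reading. 7 + 21 = 28 most naturally splits Cycle 1 into ramp-up and target-dose periods, in line with the separate ramp-up presentation in SAP 5.6, and then only the 28 remains.

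It is tempting to say that actual treatment duration carries the same excess. That is not established: SAP 5.6.1.1 removes planned breaks in dosing from actual duration, and the tail after the last dose might be removed that way.

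Nor is unequal duration for equal dosing an error in itself. Any rule that stops at death produces it. With the add-on set to 7, a last dose on Day 22 gives 24 days if the patient dies on treatment on Day 24 and 28 if the patient simply stops.

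Finally, a reader might infer an undeclared departure from Protocol 9.4.1. The formula there may define time on study only, so what can be said is that the two documents need to be reconciled.

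**Conclusion.** The point holds as an internally contradictory definition whose printed default does not fit the schedule. On weekly dosing the default exceeds the rule's own next-dose wording by 21 days (0.69 months) in each affected patient: 49 against 28 days at one cycle, 77 against 56 at two, 189 against 168 at six. Nothing later in the SAP corrects it.

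The result assumes that treatment ended for a reason other than death or data cut-off, and that the cut-off sub-rule covers only patients still on treatment then, which the SAP does not say outright.

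The reach is narrow: descriptive summaries of total duration, and of actual duration unless the tail is removed. Relative dose intensity runs only to the last dosing day and is untouched. So are total drug received, cycle counts, adverse event percentages, DLT and MTD results, ORR, PFS and OS. Duration of exposure is not a listed endpoint and no hypothesis is tested. It is worth correcting because it is cheap, not because a conclusion depends on it.

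**What to change.** - In SAP 5.6.1.1, replace the 28/7/21 text with: last date with a dose above zero, plus the days to the next scheduled dose under the schedule in force, minus the first dose date, with the last day counted no later than death or data cut-off. For a last dose on Day 22 of weekly dosing this gives 22 + 7 − 1 = 28 days.
- List the Module 1 intervals in SAP 11.7.1, taken from the schedule each cohort follows (at present 3 and 4 days in ramp-up, 7 weekly, 14 if 2-weekly). Protocol 10.6.6.1 lets the schedule change by cohort, so they belong in the module.
- Keep the death/cut-off sub-rule unchanged for patients still on treatment at that date, including those on a dose hold, and state that it applies only to them. Extending the new formula to them would change their results: with the last dose on Day 22, a hold, and cut-off on Day 40, the sub-rule gives 40 − 1 + 1 = 40 days and the new formula 28.
- If 7 and 21 only split Cycle 1 for the ramp-up presentation, say so there.
- Reconcile the definition with Protocol 9.4.1.

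The cost is one paragraph, the module intervals and one derivation line. No new data are needed, since SAP 5.6.1.2 already derives dose delays from scheduled dosing dates. Compared with the printed default, reported durations become shorter for patients who stopped treatment before death or cut-off.

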5.6.1.2 Presentation

The total and actual duration of exposure to study treatment in months will be summarised by descriptive statistics and by frequency. Dose intensity will be summarised by descriptive statistics. Exposure to investigational product (IP)(s) i.e. total amount of study drug received will be listed for all patients. Exposure swimmer plot(s) will be produced, with a line presented for each patient to display relevant exposure and disposition details.

Dosing deviations for study treatment (s) will be summarized with reasons for deviations for the following categories: reductions and interruptions. Dosing delays will be derived based

on the scheduled dosing dates using the previous dose given as reference. The number of patients with dosing delays and total dose delays will be summarised.

The number of cycles of dose received will also be summarised.

5.6.2 Adverse Events

5.6.2.1 Definitions and Derivations

The latest or current version of MedDRA will be used to code the adverse events (AEs). AEs will be graded according to the National Cancer institute Common Terminology Criteria for AEs (using the CTCAE version 5.0).

AEs are defined as treatment emergent if they onset or worsen (by investigator report of a change in intensity/severity), during the treatment emergent phase defined below.

Worsening is determined by comparison with the pre-treatment severity of the AE recorded closest to the start of dosing.

When assigning AEs to the relevant phase of the study the following rules apply and any deviations must be agreed by the study team:

- Pre-treatment phase – All AEs with a start date after signing the informed consent form (ICF), prior to the first administration of IP that do not subsequently go on to worsen during the treatment emergent phase.
- Treatment emergent phase – All AEs starting or worsening (severity) following the first administration of IP for the duration of the treatment period, up to and including 30 days after the last dose of the study treatment as per the study safety follow-up period but prior to subsequent cancer therapy. AEs with missing start time which occur on the same day as first IP administration will be reported as treatment emergent. Note that the treatment emergent phase includes the on treatment and safety follow-up periods.
- Off-treatment phase – All AEs starting more than 30 days after last dose of study treatment or once subsequent cancer therapy is started, whichever is earlier.

Serious Adverse Events (SAEs)

A serious adverse event (SAE) is an AE that fulfils one or more of the following criteria:

- Results in death
- Is immediately life-threatening
- Requires in-patient hospitalisation or prolongation of existing hospitalisation
- Results in persistent or significant disability or incapacity.

- Is a congenital anomaly or birth defect in offspring of the patient
- Is an important medical event that may jeopardise the patient

AEs of special interest

An adverse event of special interest (AESI) is one of scientific and medical interest specific to understanding of the IP and may require close monitoring and rapid communication by the investigator to the sponsor.

The following events will be considered to be AESIs:

- Tumour lysis syndrome
- Hepatotoxicity, including potential Hy's Law, Drug-induced liver injury, Bilirubin increases with transaminase (ALT or AST, or both ALT and AST) increase
- QRS amplitude shortening

Other categories may be added, or existing terms may be modified as necessary. An AstraZeneca medically qualified expert after consultation with the Global Patient Safety Physician has reviewed the AEs of interest and identified which higher-level terms and which preferred terms contribute to each AESI. Further reviews may take place prior to database lock (DBL) to ensure any further terms not already included are captured within the categories.

Other significant adverse events (OAE)

During the evaluation of the AE data, an AstraZeneca medically qualified expert reviews the list of AEs that were not reported as SAEs and AEs leading to discontinuation of study treatment. Based on the expert's judgement, AE of particular clinical importance may, after consultation with the Global Safety Physician, be considered other significant adverse events (OAEs) and reported as such in the Clinical Study Report. A similar review of laboratory values, vital signs, ECGs, and other safety assessments will be performed for identification of other significant adverse events. This review takes place prior to database lock, and any AEs identified will be fully documented in meeting minutes. Further review following database lock may result in ad-hoc OAEs being identified, in this case, the other OAEs and resulting summaries will be fully documented in the CSR.

Examples of these are marked haematological and other laboratory abnormalities, and certain events that lead to treatment (other than those already classified as serious), dose reduction or significant additional treatment.

5.6.2.2 Presentation

All AEs reported in the treatment emergent phase will be summarised and listed. Pre-treatment AEs and off-treatment AEs will be listed.

Treatment emergent adverse events (TEAEs) will be counted once for each patient for calculating percentages of patients experiencing TEAE. In addition, if the same TEAE occurs multiple times within a particular patient, the highest severity and level of relationship observed will be reported. For tables by MedDRA system organ class (SOC) and MedDRA preferred term (PT), patients with multiple TEAEs will be counted once for each SOC/PT.

An overall summary table of the number of patients experiencing each category of adverse events will be produced. The number of patients experiencing TEAEs by MedDRA SOC and PT will be summarised and the type of incidence, severity, and relationship to IP will be summarised. Further splits by CTCAE grade, causal relationship to IP and adverse events with Grade 3-4 will also be also summarised.

Separate tables present adverse events leading to discontinuation, serious adverse events, IP-related adverse events, and other significant adverse events.

Details of any deaths will be summarised and listed for all patients. AEs leading to death will also summarised.

The following summaries for the number and percentage of patients with AEs will be created by dose level/cohort and overall as appropriate:

- All AEs in any category
- AEs by SOC and PT
- AEs by SOC, PT and maximum reported CTCAE grade
- AEs above 5% of patients by PT (percentage for the threshold may be adapted as appropriate)
- AEs assessed by investigator as possibly related to study treatment by SOC and PT
- AEs leading to hospitalisation, by SOC and PT
- AEs by PT and maximum reported intensity
- AEs by PT and relationship to study treatment
- AEs leading to discontinuation of study treatment by SOC and PT
- AEs leading to discontinuation of study treatment assessed by investigator as possibly related to study treatment by SOC and PT
- AEs assessed by investigator as possibly related to study treatment by SOC, PT and maximum reported CTCAE grade.
- AEs of CTCAE grade 3 or higher assessed by investigator as possibly related to study treatment by SOC and PT Note: For patients who have a dose modification, all AEs (due to drug or otherwise) will be assigned to the initial dose group.

- AEs leading to study treatment interruption (infusion interruption or missed dose) by SOC and PT
- Non-serious AEs occurring in greater than 5% of patients
- SAEs by SOC and PT

SAEs

SAEs will be summarised as described above for the TEAEs.

AEs of special interest

Grouped summary tables of certain MedDRA preferred terms will be produced and may also show the individual preferred terms which constitute each AESI grouping. Groupings will be based on preferred terms provided by the medical team prior to DBL, and a listing of the preferred terms in each grouping will be provided.

Summaries of the above-mentioned grouped AE categories include number and percentage (%) of patients who have:

- At least one AESI presented by event outcome
- At least one AESI causally related to IP
- At least one AESI leading to discontinuation of study treatment.

A summary of total duration (days) of AESI will be provided for events which have an end date, and this may be supported by summaries of ongoing AESIs at death and, separately, at data cut-off.

